### Hypotheses:

We hypothesize that with greater discount levels, there will be progressive increases in purchasing and intake of F&V and non-caloric beverages during the intervention period as well as improvement in health outcomes, which will be partially sustained during the follow-up period.

We predict greater relative increases in purchasing and consumption of F&V and improved health outcomes, among those with lower incomes as compared to those with higher incomes. F&V prices are relatively high compared with other foods, and are less affordable to those of lower income, who would be expected to benefit more from price reductions.

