### Specific Aims:

For the aims below, the first outcome (underlined) within each aim is primary, and the other outcomes are secondary.

**Primary Aim 1:** To investigate the effects of multi-level discounts on behavioral and health outcomes during the intervention period and their sustained effect during the follow-up period.

For greater price discounts ( $30\% > 15\% > 0\%$  group), we predict:

- a. *Purchasing Behaviors*
  - i. higher individual gross purchasing (i.e., price before discount) of F&V and non-caloric beverages
  - ii. reduced individual gross purchasing of less healthy, high energy dense (ED) highly processed foods (e.g., processed bakery items)
- b. *Consumption Behaviors*
  - i. higher individual F&V intake (g), the primary outcome measure (used to power the study), as assessed by 24-h dietary recalls and Brief Block Food Frequency Questionnaires (FFQ) (confirmed by biomarkers: plasma carotenoids and Vitamin C), as well as greater intake of non-caloric beverages
  - ii. decreased high energy-dense (ED) food intake (g), lower total fat intake (g), and lower daily energy intake (kcal)
- c. *Health Outcomes*
  - i. lower body weight (kg) and BMI ( $\text{kg}/\text{m}^2$ ), lower % body fat
  - ii. improved metabolic syndrome risk factors (fasting glucose, blood lipids, blood pressure)

	Protocol Name:	Multi-level supermarket discounts of fruits and vegetables on intake and health
	Principal Investigator:	[name]
	Primary Contact Name/Contact Info:	[name] [contact] [name] [contact]
	Date Revised:	8/7/20
	Study Number:	HS#: 16-00407 GCO#: 16-1050

**Primary Aim 2:** To investigate the effects of income as a moderator of outcome measures.

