renowned health economist specializing in obesity is a consultant to the application. We will estimate demand for F&V by regressing the level of purchasing and consumption against discount price levels. We will also assess the impact of each discount level on changes in individual health-related measures (weight, BMI, % body fat, systolic and diastolic blood pressure, fasting HDL cholesterol, triglyceride, CRP, HbA1c, and fasting blood glucose) and on the composite metabolic syndrome. We will also examine the supermarket's net profit (difference between real cost and selling price of each food item or the profit margin) at each discount level. Although larger discounts might be expected to result in reduced profit margins, the losses may be offset by more frequent shopping, leading to purchases of other non-subsidized products with higher profit margins. Effects of the discount level on net profits will be useful in encouraging store owners to adopt discounts.

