### **Preliminary Study**

The preliminary study findings were published electronically in July 2013, and then in print in the December 2013 issue of the journal *Obesity*. The preliminary study was funded by a seed grant from Columbia University's Institute for Social and Economic Research and Policy and the Robert Wood Johnson Foundation. The CEO of D'Agostino Supermarkets, [name], granted access to office resources in two Manhattan supermarkets, and graciously declined reimbursement for the cost

	Protocol Name:	Multi-level supermarket discounts of fruits and vegetables on intake and health
	Principal Investigator:	[name]
	Primary Contact Name/Contact Info:	[name] [contact] [name] [contact]
	Date Revised:	8/7/20
	Study Number:	HS#: 16-00407 GCO#: 16-1050

incurred by the discounts.

**Methods and Participants:** The study comprised a 4-wk baseline, an 8-wk discount intervention, and a 4-wk follow-up with no discounts. Following the baseline period, Ss were randomized into two groups: a 50% discount on select F&V and non-caloric beverages, or no discount. All subjects received new D'Agostino Rewards scan cards to track purchasing and to implement discounts. Type, quantity, and cost of purchased items were based on data from scans of the bar codes. Overweight and obese (BMI $\geq$ 25-40) shoppers were recruited from two D'Agostino Supermarkets, and n=47 (33 f, 14 m) was used for analysis. Age, BMI, income, and % gender did not differ between intervention groups, and the sex ratio was about 3:1; f:m. Household incomes had a good spread between \$10,000 and \$150,000.

**Results:** Purchasing of F&V. During the intervention period, gross weekly purchasing of F&V by the discount group was nearly 3 times that of the control group. Purchasing of F&V increased from baseline to intervention,  $P<0.0001$ , and then decreased from intervention to follow-up,  $P=0.002$ , but remained higher than at baseline,  $P=0.01$ . Gross purchasing of F&V did not change significantly for the control group. Income (mean by income bracket) was inversely related to F&V purchasing in the discount group during the intervention,  $r = -0.75$ .

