  - Medical Diagnoses: uncontrolled diabetes, chronic organ failure (heart, lung, kidney, pancreas, etc.), inflammatory conditions (irritable bowel syndrome/disease, chronic malabsorptive diseases), hypertension >140/90 at the Screening Visit, HIV/AIDS, current serious STD, cancer (or < 5 years cancer free), major surgery within the previous 3 years, or other chronic disease which may impact weight status.
  - Psychiatric Diagnoses: severe depression, bipolar disorder, schizophrenia, dementia, eating disorder, or any other psychiatric condition which may impact typical intake of foods/fluids.
- Dependent on or abusing alcohol or other drugs, or not drug-free/sober for at least 6 months
- Currently receiving governmental discounts on fruits/vegetables (i.e., SNAP, WIC)
- Physical disability impacting safety of study procedures/tasks
- Has a chronic disease or takes medications that can put the individual at increased risk for a severe COVID-19 infection

Protocol Name:	Multi-level supermarket discounts of fruits and vegetables on intake and health
Principal Investigator:	[name]
Primary Contact Name/Contact Info:	[name] [contact] [name] [contact]
Date Revised:	8/7/20
Study Number:	HS#: 16-00407 GCO#: 16-1050

Several exclusions, such as serious disease, change in medications, or use of illicit drugs will help limit confounding influences on body weight and health outcomes. We will recruit weight-stable overweight and obese subjects, a group that generally reports low consumption of F&V. Increasing F&V intake in this overweight group is likely to lead to relatively greater health benefits and possible weight reduction than in those of normal weight, who are more likely to be consuming adequate F&V. The participant should be the main shopper who is already purchasing at least 30% of food at a given Allegiance affiliate supermarkets and is consuming at least 50% of the food purchased. We will include subjects who dine out (or order take-out) for lunch or dinner up to 5 times/wk. The primary food shopper and consumer will be the unit of analysis.

Review of the rate of subject accrual and adherence to inclusion/exclusion criteria will occur bimonthly during the recruitment period. This will assure that participants will meet eligibility criteria and ethnic diversity goals outlined in the grant application.

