Multi-level Supermarket Discounts of Fruits and Vegetables' Impact on Intake and Health
PI: [name]
NCT04178824
Document Date: 8-1-2023

Statistical Analysis Plan

Linear mixed effects modeling was performed to evaluate the group-by-time interaction of all outcomes from the intent-to-treat (ITT) sample, as a primary analysis, and the per-protocol sample, as a secondary analysis. The ITT sample was comprised of participants with at least one post-randomization measurement. The per-protocol sample was comprised of all participants who completed the study. Primary outcome measures were grams (g) of fruit, vegetable, non-caloric beverage intake, and body weight (expressed in kilograms (kg)). Secondary dietary outcomes were high-ED food intake (g), total fat intake (g), and daily energy intake (kcal). Secondary clinical outcomes were BMI (kg/m²), percent body fat, waist circumference (cm), metabolic risk factors (fasting glucose (mg/dL), cholesterol (mg/dL), and blood pressure (mmHg). The linear mixed model included the group-by-time interaction term, where time was the within-subjects factor and group was the between-subjects factor (fixed effects), and the participant as the random effect to obtain the within-person differences in response to the intervention. No covariates were added to the main model because there were no baseline differences in covariates between discount groups and the RCT study design reduces between-group differences (29). First, an omnibus test was performed to test the overall effect of the group-by-time on interaction on the outcome variables. Then, a planned comparison approach using difference-in-difference contrast (DiD) was done to evaluate the differential change in primary outcome variables. The main comparison of interest was the change between groups between the baseline and the first 16 weeks of the intervention (the mid-point of the intervention period), 32 weeks of the intervention (the end of the intervention period), and 16 weeks post-intervention (the end of the follow-up period). A sensitivity analysis was also performed on the ITT sample by adding key covariates to the model: sex, age at enrollment, season at enrollment, primary supermarket, COVID presence, and income level. The presence of COVID was assigned if the COVID-19 pandemic and lockdown period occurred during the intervention between 2/20/20 and 4/6/2021. The absence of COVID-19 was assigned if the COVID-19 pandemic period happened prior to or after the intervention. Income level was a dichotomous variable: above or below the median income in NYC. Estimated means and 95% confidence intervals are shown in tables and figures. Missing data was assumed to be missing at random (MAR). Two-tailed $P < .05$ was considered statistically significant. RStudio (RStudio version 2023.12.0 Build 369) was used to analyze all data.

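### The SAP specifies no analysis that estimates income moderation (Primary Aim 2): income is only a binary covariate in a sensitivity model

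*SAP*

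**What the plan says.** **Protocol.** Under Specific Aims, Primary Aim 2 reads "To investigate the effects of income as a moderator of outcome measures". The Hypotheses section gives it a direction: "We predict greater relative increases in purchasing and consumption of F&V and improved health outcomes, among those with lower incomes". Income is collected by questionnaire (Appendix B) around Study Visit 1. The protocol gives no statistical method for this aim. Its one regression statement, in the economic analysis within Background Significance, is "We will estimate demand for F&V by regressing the level of purchasing and consumption against discount price levels", with no mention of income.

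**SAP.** The main model is a linear mixed model with group, time and their interaction, a participant random effect and no covariates. An omnibus test of that interaction is followed by difference-in-difference (DiD) contrasts between discount groups: "The main comparison of interest was the change between groups between the baseline and the first 16 weeks of the intervention", with further contrasts at the end of the intervention and at the end of follow-up. The analyses are run on the ITT sample and, secondarily, on the per-protocol sample.

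Income enters once: "A sensitivity analysis was also performed on the ITT sample by adding key covariates to the model". The list is sex, age, season, supermarket, COVID presence and income, and on the last of these, "Income level was a dichotomous variable: above or below the median income in NYC". The SAP mentions neither moderation nor Aim 2.

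**The concern.** One of the trial's two primary aims has no estimand, estimate or interval in the analysis plan, and nothing says that it was dropped, deferred or made exploratory. Part of the trial's rationale is that fruit and vegetables (F&V) are less affordable at lower income, so that lower-income shoppers should gain more from a discount. Followed to the letter, the plan cannot confirm or contradict that.

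There is also a risk of misreading. Because the sensitivity model contains income, a report could appear to have dealt with Aim 2 when it has only adjusted for income.

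The single income result in the documents cannot stand in for the missing one. It comes from the preliminary study: "Income (mean by income bracket) was inversely related to F&V purchasing in the discount group during the intervention", r = -0.75. It is a correlation within the discounted arm, with no matching control-arm figure, so it does not show that the effect of the discount varies with income.

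**Working it through.** **1. What Aim 2 needs, against what the SAP lists.** Let d_L and d_H be the DiD (discount arm versus 0%) for people below and above the income cut. Aim 2 is about d_L - d_H.

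| SAP component | Contains income crossed with group? |
|---|---|
| Main mixed model (group, time, group-by-time) | No; no covariates |
| Omnibus test | No; tests group-by-time |
| DiD contrasts at three time points | No; between discount groups |
| Per-protocol repeat | No |
| ITT sensitivity model, six added covariates | No interaction stated |

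None of these estimates d_L - d_H, and the protocol supplies no such analysis either.

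**2. Why adjusting for income does not help.** In the adjusted model the income term is g x inc_i, the same for person i at every visit. In the change from baseline to time t it becomes g x inc_i - g x inc_i = 0. With complete data the DiD is therefore the same with or without the term.

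If income does moderate the effect, and a share p of each arm is below the cut, both models estimate

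DiD = p x d_L + (1 - p) x d_H.

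This is one number for two unknowns. With assumed effects in SD of change and p = 0.5:

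- 0.46 and 0.46 give 0.46.
- 0.92 and 0 give 0.5 x 0.92 = 0.46.
- 0 and 0.92 give 0.46.

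The three patterns coincide only because p was set at 0.5. At p = 0.2 the last two give 0.2 x 0.92 = 0.18 and 0.8 x 0.92 = 0.74. In no case can d_L - d_H be recovered from the average alone. With missing visits the adjusted DiD can shift, but the model still has no parameter through which income alters the discount effect.

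One simulated dataset (75 per arm, true effect 0.8 in one stratum and 0 in the other) illustrates this. The DiD was 0.300 (SE 0.163) with and without the income term. The three-way term was 0.707 (SE 0.320).

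**3. Precision if the term is added.** The documents state no power, effect or SD for Aim 2, so there is no figure to reproduce. Assumptions: n per arm in equal arms, change SD 1, two-sided alpha 0.05, and the same share p in both arms.

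- SE of the pairwise contrast = sqrt(2/n).
- SE of the income difference = sqrt(2/(np) + 2/(n(1 - p))).
- Ratio = 1/sqrt(p(1 - p)), which does not depend on n.
- Power for an interaction as large as a main effect detectable at 80% power = Phi(2.802/ratio - 1.96) plus a negligible opposite tail, where 2.802 = 1.960 + 0.842.

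| Income split | SE ratio | Power |
|---|---|---|
| 50:50 | 2.00 | 29% |
| 30:70 | 2.18 | 25% |
| 20:80 | 2.50 | 20% |

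The 95% half-width for the income difference is 1.96 x ratio x sqrt(2/n). The ITT size is not given, so two protocol figures serve as markers: the planned 225 completers (360 x 0.625), or 75 per arm, and all 360 enrolled, or 120 per arm.

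- 50:50: 1.96 x 2.0 x 0.1633 = 0.64 SD at n = 75; 1.96 x 2.0 x 0.1291 = 0.51 SD at n = 120.
- 20:80: 0.80 SD and 0.63 SD.

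**4. Time points.** The SAP's contrasts fall at weeks 8 + 16 = 24, 8 + 32 = 40 and 40 + 16 = 56. The protocol's Endpoints section names weeks 40 and 56 as primary.

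**The case against.** **Adding covariates might include interactions.** The text does not say so. Income is listed beside five other adjustment variables, and where the SAP intends an interaction it names it.

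**The test is too imprecise to be worth specifying.** The low power is real and stands. It argues for reporting an interval and reading it cautiously. It does not argue for leaving a primary aim unmentioned.

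**A full three-way analysis invites many comparisons.** This stands. With baseline and three later times, the interaction has 2 x 3 x 1 = 6 degrees of freedom. There are 3 pairs x 3 times = 9 income differences per outcome, or 36 over four outcomes if fruit and vegetables are taken separately. One contrast has to be named in advance of the others.

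**Stronger readings that the documents do not support.**

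- A reader might infer that Aim 1 is compromised. It is not: the average discount effect is a valid target with or without moderation.
- A reader might infer that Aim 2 was abandoned. The documents are only silent. If it is handled elsewhere, a cross-reference would close the point.
- A reader might call any added analysis purely post hoc because the SAP is in the past tense. The hypothesis and its direction are in the protocol; only the method would be new.
- A reader might infer that excluding recipients of SNAP or WIC discounts leaves few people below the income cut. The documents give no income distribution, so the split is unknown.

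**Conclusion.** The gap is real and rests on the text alone: the SAP specifies no analysis of Primary Aim 2. The income-adjusted sensitivity model carries no information on moderation. That is exact with complete data, and with missing visits the model still returns only an average effect. This is an omission from the plan and from what would be reported; it introduces no bias into Aim 1.

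The hypothesis also covers purchasing, which has no outcome in the SAP, so an income term on the SAP's primary outcomes alone would leave that part unanswered.

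The precision figures depend on equal arms, equal variances and an assumed income split. Randomisation is stratified by gender within store and not by income, so the split may also differ between arms. Within those assumptions, power is about 29% at 50:50 and 20% at 20:80, and a null result would not show absence of moderation.

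**What to change.** Either specify the analysis or disclose that it was not done.

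**To specify it:**

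- In the ITT mixed model for the SAP's primary outcomes, add a group-by-time-by-income interaction. Use the NYC-median split, and a finer income measure as well if the questionnaire recorded one.
- Name one key contrast, 30% versus 0% at week 40 for F&V intake, and treat all other contrasts as supportive.
- Report the DiD in each income stratum and their difference, with 95% confidence intervals.
- State whether the comparison is absolute or relative. The hypothesis speaks of relative increases, while a DiD in grams is absolute, and the two can disagree if baseline intake differs by income.
- State that purchasing has no outcome in the SAP. Either apply the same income analysis to it or disclose that this part of the hypothesis was not analysed.
- Label the work as a protocol-stated hypothesis whose method was specified after the current SAP.

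**Otherwise,** state that Primary Aim 2 was not analysed, and do not present the income-adjusted model as addressing it.

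**Cost.** The data are already collected under the protocol and no new visits are needed. The price is one further model per outcome, more contrasts to rank, and wide intervals that must be reported as such. The disclosure option costs one sentence.

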### c) Number of Subjects

We will recruit 360 overweight and obese (BMI 24.5-40) subjects, and estimating a 37.5% dropout rate, this should lead to 225 completers.

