**NIH**

**Part II. Data Monitoring Committee/Data Safety Monitoring Board (DMC/DSMB)**

**N/A**

**6) Withdrawal of Subjects**

Data from subjects who show little or no purchasing for 8 weeks will be dropped from the study. Otherwise, no pressure will be exerted on the subjects to participate, and they have the right to withdraw from the study at any time. Once an issue is identified, subjects will be contacted by the research team. If there is not resolution of the issue within the following week, the subject will be removed (dropped) from the study, and their discounted card (when applicable) will be deactivated. Data will be analyzed for participants with complete data sets up through Study Visit 3 (week 24). Participants with fewer data points due to drop-out will not be included in analyses.

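### The SAP's intent-to-treat model assumes MAR for participants whose discount card is switched off on removal, so it targets a continued-discount effect that is likely to exceed the effect of assignment

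*SAP*

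**What the plan says.** The SAP's primary analysis is a linear mixed model with a group-by-time term and "the participant as the random effect to obtain the within-person differences in response to the intervention". It is run on a sample labelled intent-to-treat: "The ITT sample was comprised of participants with at least one post-randomization measurement". On missing data it says only "Missing data was assumed to be missing at random (MAR". Two other analyses are described. One is a per-protocol analysis of completers. The other is this: "A sensitivity analysis was also performed on the ITT sample by adding key covariates to the model". Neither changes the missing-data assumption, and no estimand is stated.

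Protocol section 6 (Withdrawal of Subjects) drops people with little or no purchasing over 8 weeks. It also says that if an identified issue is not settled within a week, "the subject will be removed (dropped) from the study, and their discounted card (when applicable) will be deactivated". No measurement after removal is described. The same section restricts the analysis set: "Data will be analyzed for participants with complete data sets up through Study Visit 3 (week 24". Those who drop out with fewer data points are left out of the analyses.

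On expected loss, Protocol section 5c has 360 recruits, "estimating a 37.5% dropout rate, this should lead to 225 completers". The Brief Summary says that no discount is in force in the baseline or follow-up periods, so the discount runs from week 8 to week 40.

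**The concern.** Under MAR, the mixed model treats a removed person's later visits as following the course of people in the same arm with similar earlier data. In the 15% and 30% arms, those people still have the price cut and the removed person does not. In the control arm there is no such break, because removal does not change the price that a control participant pays. The model therefore answers what would have happened had the discount continued for everyone. An intent-to-treat label suggests something else: the effect of being assigned the discount, whatever happened afterwards.

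The pilot suggests that the two differ. In the Preliminary Study section, purchasing of fruit and vegetables (F&V) fell once the discount stopped. One stated ground for being dropped, little or no purchasing, also describes people who make little use of a discount. Purchasing is not in the SAP's model for intake or weight, so that ground also makes MAR harder to defend.

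At stake is how the week-24 and week-40 results are read. Protocol section 2 says that the main aim is to encourage government subsidies. A reader who takes the reported estimate as the effect of offering a discount may take it to be larger than it is, and no planned analysis would show by how much.

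**Working it through.** **1. The plan's own figure.** 360 × (1 − 0.375) = 225 completers, which reproduces section 5c. (Section 5a gives 20% and 240 completers. 360 × 0.80 = 288, so that pair does not reproduce. This is a separate inconsistency.)

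**2. Visits affected.** Week 24 and week 40 fall in the discount period. Week 56 does not.
- Everyone in the SAP's sample has at least one post-randomisation measurement, so most of the missing values at issue are at week 40.
- A week-24 value can be missing in that sample if membership rests on another measurement, such as a dietary recall taken between visits. The SAP does not say whether the qualifying measurement must be of the outcome analysed.
- Under section 6's rule, week 24 would be complete for everyone analysed, and only week 40 would be affected.

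**3. Formula.** Let D be the effect with the discount continuing, q the share of a discount arm lost after randomisation and before the visit, and r the fraction of effect kept once the card is off. Assume that removal is unrelated to response.
- The MAR model targets D.
- Effect of assignment = (1 − q)D + q·r·D = D[1 − q(1 − r)].
- Ratio of the two = 1/(1 − q(1 − r)).

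**4. Values for q (assumed; the documents give none).** The 37.5% counts loss from enrolment. If k of the 135 expected losses come before randomisation, loss among those randomised is (135 − k)/(360 − k). This is 37.5% at k = 0 and falls as k rises; for example, k = 45 gives 90/315 = 28.6%. So 37.5% is an upper bound on the planned loss averaged over arms, and 10% and 20% show the lower range.

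**5. Values for r (assumed).** In the pilot, the F&V share of purchasing in the discount group went from 7% to 20% to 14%. The retained fraction is (14 − 7)/(20 − 7) = 7/13 = 0.54. That comes from a 50% discount and a 4-week follow-up, and it concerns purchasing, not intake or weight. The ends of the range are r = 0 and r = 1.

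**6. Results.**

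| q | r = 0 | r = 0.54 | r = 1 |
|---|---|---|---|
| 10% | 1/0.90 = 1.11 | 1/(1 − 0.10 × 0.46) = 1.05 | 1.00 |
| 20% | 1/0.80 = 1.25 | 1/(1 − 0.20 × 0.46) = 1.10 | 1.00 |
| 37.5% | 1/0.625 = 1.60 | 1/(1 − 0.375 × 0.46) = 1.21 | 1.00 |

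**7. Rough check.** A small simulation of a random-intercept model (1,500 per arm, assumed SD 1 and effect 0.4, four replicates per setting) gave week-40 ratios of 1.17 at q = 20% and 1.54 at q = 37.5%, both with r = 0. The formula gives 1.25 and 1.60. With so few replicates the gaps are within simulation noise, and the formula is the main result.

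**The case against.** A good deal of the case on the other side stands.

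- **The model is not a completer analysis.** A reader might infer that it estimates the effect only in people who still hold a working card. It does not: it uses every observed visit, including those of people removed later. The completer analysis is the per-protocol one.
- **Overstatement is not demonstrated.** A reader might infer that the result is inflated by up to 60%. That needs the largest q and no carry-over at all. The protocol's hypotheses and the pilot both point to partial carry-over, and an immediate loss of the whole effect is a strong assumption for body weight. Removal that is related to outcome, or that differs by arm, could move the estimate either way.
- **The loss share is uncertain.** Participants learn their group at week 8, and section 5f withdraws low spenders and people who cannot be reached during baseline. Section 5e ties the low-purchasing rule to the first 8 weeks, while section 6 does not, so how often it applies after randomisation is unclear. Deactivation is explicit for removal over an unresolved issue, but not for voluntary withdrawal.
- **Week 56 is different.** No arm has a discount then, so a removed participant differs only in having had a shorter exposure. Imposing the control profile there would assume away the carry-over that the visit is meant to measure.
- **The policy question may favour the MAR target.** A subsidy would not stop because someone left a study, so the continued-discount effect is arguably the relevant one. This is why the documents do not support replacing the headline estimate with a reference-based one.

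None of this removes the central point. The target is unstated, the label suggests a different one, and the assumption that separates the two is not tested.

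**Conclusion.** The concern holds in a limited form. For participants in the SAP's sample who are removed from a discount arm, missing week-24 and week-40 values are modelled as if the discount had continued. The estimate is therefore of a hypothetical continued-discount effect. It is likely, but not certain, to exceed the effect of assignment. Full carry-over, the case with no difference, does not fit the pilot's fall in purchasing after the discount ended.

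With the pilot's retained fraction, the illustrative excess is about 5% to 21% for q from 10% to 37.5%. With no retention it is 11% to 60%, and with full carry-over it is nil. These figures rest on assumed q and r, and on removal being unrelated to response. The documents give no removals by arm or reason.

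The sample is a second, more direct departure from intent-to-treat. The SAP leaves out anyone without a post-randomisation measurement, and section 6 would also leave out those without complete data through week 24. The two rules do not agree, and imputation within either sample does not restore the people left out.

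**What to change.** In the SAP:

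1. Describe the MAR mixed-model result as the effect under continued availability of the discount.
2. Add a sensitivity analysis for F&V intake and body weight at weeks 24 and 40: reference-based multiple imputation of post-removal visits in the 15% and 30% arms. Use jump to reference (the control-arm profile, r = 0) as the conservative end, and add a partial-retention or delta-adjusted version. The SAP is written in the past tense, so mark this analysis as an addition.
3. Report removals and withdrawals by arm, reason and time, so that q can be read from the data.
4. State any claim about the effect of offering a discount in light of both results.
5. Reconcile section 6's exclusion of participants without complete data through week 24 with the SAP's sample definition, and say which was used.

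The cost is some SAP wording, a short imputation program and one table, with no new outcome data. The downside is that the reported range may include a smaller effect than the MAR estimate alone.
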